In addition to data retrieved from patients' hospital records, we plan to retrieve data on hospital admissions during follow-up from the Norwegian Patient Registry (NPR). As described, information regarding cancer diagnosis and treatment, survival and death will be extracted from patient records, but we also plan to obtain data from the Norwegian Cancer Registry (cancer diagnosis, stage of disease and treatment) and The Norwegian Cancer Registry (date, place and cause of death) to ensure data quality. Survival data will contribute to identify patients with short life expectancy, who potentially may benefit more from purely palliative measures than from a GAM intervention.

Implementation

Enrolment

A project nurse will have the daily responsibility for all data collection.

All patients who are 65 years or older and have been referred to the Radiotherapy Unit, SI Gjøvik, will receive brief information about the study together with the letter summoning them to their first consultation. This consultation is usually meant for information and treatment planning (CT dose planning), whereas the treatment itself normally starts several days, sometimes weeks, later. Eligible patients will be identified at the first consultation. The treating oncologist will ensure that the inclusion criteria are fulfilled, and **that the patient is capable of providing informed consent**. The project nurse will present the study for the patient both orally and in writing. If the patient consents to participation, baseline registrations will be performed on the same day (i.e. if the EBRT is expected to start within one week), or in connection with start of treatment.

Baseline registrations (i.e. the GA) includes a test of cognitive function (MoCA test). If the MoCA score is below 20 (possible dementia), the patients' treating oncologist will be consulted to re-evaluate the patients' capability to give informed consent before the baseline procedures are completed. However, since patients with mild to moderate dementia may also have sufficient capability to provide an informed consent, no definite MoCA score limit is set for inclusion/exclusion.

Baseline registrations include a test of cognitive function (MoCA test). If the test gives reason to believe that the patient has cognitive impairment (score ≤ 18), and the project nurse (an

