~~Patients who have received less than 10 radiation fractions (treatment duration two weeks or less), will only fill in the self-report questionnaire since a new GA after such a short period is likely to add little new information.~~

Further follow-up

The self-report questionnaires, scheduled at 2, 8 and 16 weeks after completion of EBRT, will be administered by post to all patients with a prepaid return envelope attached. If no answer is received within 2 weeks, a reminder will be sent.

Apart from this, the follow-up will vary somewhat depending on whether the health services in the patients' municipality have consented to participate with GA or not.

1. For patients from non-consenting municipalities who does not have any contact with the municipal home care services, the project nurse will offer to contact them (or the municipal cancer contact nurse) by the end of EBRT. The purpose is to ensure that the patient receives a follow up according to the municipality's routine.

Moreover, for these patients, a few questions will be added to the self-report follow-up questionnaires. The patients will be asked if they have any questions or needs that makes a phone call from the project nurse or a cancer nurse at the Radiotherapy Unit warranted, and about their use of municipal health care services. If the information about the latter is lacking or incomplete, the project nurse will take contact with the municipality services directly.

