Primary: Global quality of life (QoL) and physical function as assessed by the European Organisation for Research and Treatment of Cancer Quality of Life Questionnaire (EORTC QLQ-C30) global QoL (gQoL) and physical functioning (PF) scale.

Secondary:

- Instrumental Activities of Daily Living (ADL)-function assessed by Nottingham Extended Index of Activities of Daily Living (NEADL) based on patients' self-report.
- Role function as assessed by the EORTC QLQ-C30 role function (RF) scale
- Fatigue and pain as assessed by the EORTC QLQ-C30 corresponding symptom scales (FA = fatigue)(PA = Pain)

Exploratory: Functioning and symptom scales/items of the EORTC QLQ-C30 that are not defined as primary or secondary outcomes will be assessed for explorative purposes

Hypotheses:

1. Patients referred for palliative RT have poorer scores for all primary and secondary outcomes prior to and after RT compared to patients referred for curative treatment
2. There is a significant difference in trend in outcomes for palliative and curative patients:
 - a. patients referred for palliative RT will experience an improvement in the primary outcomes global QoL and PF, and the secondary outcomes RF, NEADL and pain (PA) within 8 weeks after RT.
 - b. patients referred for curative RT will experience a deterioration in the primary outcomes global QoL and PF and the secondary outcomes RF, NEADL and

fatigue (FA) scores from baseline to 2 weeks after RT. Thereafter the scores will return to baseline values within 16 weeks.

3. There is a significant difference in trend in outcomes depending on number of geriatric impairments
 - a. scores for the primary outcomes global QoL and PF, and the secondary outcome RF decreases with increasing number of geriatric impairments
 - b. there is a significant association between number of geriatric impairments and the primary outcomes global QoL and PF as well as the secondary outcome RF scores

Timeline for the assessments: Patients answered EORTC QLQ-C30 and NEADL at five different time points: baseline, when completing RT (except palliative patients who received only a single fraction were per protocol test schedule not asked to answer EORTC QLQ-C30, and patients who received <10 fractions were not asked to answer NEADL), and 2, 8 and 16 weeks after RT. We will exclude the assessment of NEADL at the end of RT from our analyses because patients with short courses of RT did not fill in this questionnaire.

Statistical approach

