Categorical baseline characteristics of curative and palliative patients will be described with frequencies and percentages, while continuous with means and standard deviations (SD) or median and min-max values.

Raw scores for all QLQ-C30 scales/items will be transformed into scales ranging from 0-100 in accordance with the official manual for this questionnaire. NEADL item scores will be summarized into a scale ranging from 0-66. Missing NEADL items scores will be imputed as follows:

The missing values are assumed to be missing at random (MAR), and will be imputed if at least half of the items of the scale had been answered. The imputation will be performed by generating an empirical distribution for each item based on non-missing values, and a random number drawn from it was used to replace the missing value.

To answer Study aim 1 and test our first hypothesis, the primary outcomes, global QoL and PF will be assessed by linear mixed model with fixed effects for (non-linear) time, treatment group (curative vs. palliative) and the interaction between the two. Random effects for patients will be included. The models will be adjusted for age, gender, performances status (ECOG PS) and cancer type. The secondary outcomes RF, NEADL and pain scores will be evaluated by similar models.

To answer Study aim 2 and test our second hypothesis, similar models to those describe for aim 1 will be performed for the primary outcomes global QoL and the secondary outcome RF. However, these models will use number of geriatric impairments as a stratification variable instead of treatment intent (palliative vs curative). The models will be adjusted for age, gender, cancer type, treatment intent (curative vs palliative) and ECOG PS.

Sensitivity analyses to estimate models for non-imputed variables for NEADL will be also be performed.

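### Missing NEADL items get one random draw that ignores the patient's own answers; depending on an unstated choice, this shrinks the curative–palliative difference, or shifts the adjusted difference and understates its standard error

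*Combined protocol and SAP*

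**What the plan says.** Appendix 3, Statistical approach, gives this rule for missing NEADL items: "The missing values are assumed to be missing at random (MAR), and will be imputed if at least half of the items". The condition is that those items were answered. The method is: "The imputation will be performed by generating an empirical distribution for each item based on non-missing values, and a random number drawn from it". That number then replaces the missing value. There is one draw per item, with no repetition and no variance correction. The text does not say whether the distribution is formed over all patients and visits or separately by treatment intent or visit.

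NEADL is a secondary outcome of paper 3. Hypothesis 1 in Appendix 3 predicts poorer levels in palliative patients. Hypothesis 2 reads "There is a significant difference in trend in outcomes for palliative and curative patients", and both of its parts name NEADL. For the primary outcomes the plan is a linear mixed model with time, treatment group and their interaction, and "The models will be adjusted for age, gender, performances status (ECOG PS) and cancer type". Then: "The secondary outcomes RF, NEADL and pain scores will be evaluated by similar models". There is also a check: "Sensitivity analyses to estimate models for non-imputed variables for NEADL will be also be performed".

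Collection differs by visit. Under Enrolment, "baseline registrations will be performed on the same day" as consent if treatment is expected within a week, and otherwise around the start of treatment. Under Further follow-up, the 2-, 8- and 16-week questionnaires "will be administered by post to all patients with a prepaid return envelope attached".

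**The concern.** Under MAR, missingness may depend on what was observed, so a valid imputation has to use what was observed. A draw that depends only on which item is missing does not. A patient who needs help with nearly everything can receive the answer of a fully independent patient, and the reverse. The assumption and the method therefore do not match.

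At stake are the size of the curative–palliative NEADL difference (hypothesis 1), the difference in its course (hypothesis 2) and the width of the intervals. Which of these suffers depends on whether the draw is pooled over treatment groups, so both readings need to be worked through.

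**Working it through.** **Inputs from the documents.** 301 patients, 165 curative and 136 palliative (Appendix 1). NEADL range 0–66 (Appendix 3). The areas listed under Questionnaires for self-report sum to 6 + 5 + 5 + 6 = 22 items, and 22 × 3 = 66; the same paragraph says 20 items, which would give 60. I use 22. Smallest relevant change 2.4–6.1 points (same section); this is a threshold for change, so it serves only as a yardstick. The plan has no NEADL figure to reproduce.

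**Assumed.** Item-missing fractions of 2–20%, a true gap G (curative minus palliative) of 6 or 12 points, and MCAR unless stated.

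**(a) Pooled draw, level.** Imputed items have the same expected value in both groups, so observed gap = (1 − m)G and loss = mG.

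| m | loss, G = 12 | loss, G = 6 |
|---|---|---|
| 2% | 0.24 | 0.12 |
| 5% | 0.60 | 0.30 |
| 10% | 1.20 | 0.60 |
| 20% | 2.40 | 1.20 |

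A simulation of 200,000 patients with 22 items gave shrinkage of 2.0%, 4.9%, 10.0% and 20.1% at these fractions. When poorer patients skip more items, shrinkage was 3.2%, 8.2% and 16.3% at 2%, 5% and 10%.

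**(a) Pooled draw, trend.** Observed narrowing of the gap from baseline to week 8 = (1 − m0)G0 − (1 − m8)G8.
- G = 12 at both visits (no true trend difference): 5% at both gives 0. With 2% then 10%, 11.76 − 10.80 = 0.96 points of false narrowing.
- G = 12 then 6 (true narrowing 6.00): 5% at both, 11.40 − 5.70 = 5.70. With 5% then 10%, 11.40 − 5.40 = 6.00. With 2% then 10%, 11.76 − 5.40 = 6.36 (+6%).

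The bias vanishes only when m0·G0 = m8·G8.

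**Trial-size simulation.** 165:136 patients, 22 items scored 0–3, one covariate differing by 0.8 SD between groups as a stand-in for the adjusters, MCAR, and forms with more than 11 missing items dropped. OLS at baseline, and OLS on baseline-to-week-8 change as a stand-in for the mixed-model interaction. True unadjusted gap 11.05, adjusted gap 6.05. There were 300–400 repeats, and 3,000 for the null trend.

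*Pooled draw.*
- Adjusted gap: bias −0.31, −0.60, −1.24 at 5%, 10%, 20%. The formula gives 6.05m = 0.30, 0.61, 1.21.
- Level test at 10%: 9.93/1.46 = 6.8, against 11.03/1.60 = 6.9 with complete data. Estimate and standard error shrink together.
- Rejection of a true null trend difference at nominal 5%: 6% with complete data, 6% at 5% at both visits, 7.5% at 2% then 5%, and 17% at 2% then 10% (17–19% across separate codings of the model).

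*(b) Draw within group and visit.*
- Unadjusted bias: 0.00 at all three fractions.
- Adjusted gap: imputed items carry the group mean but no covariate effect, so the covariate correction of 11.05 − 6.05 = 5.00 points weakens by the fraction m. Predicted shift 5.00m = 0.25, 0.50, 1.00; simulated +0.26, +0.50, +1.00.
- Reported SE 1.48, 1.40, 1.28, against 1.53–1.54 with complete data. Coverage of the 95% interval 92%, 90%, 82%.
- If poorer patients skip more items, the large simulation still shows the unadjusted gap shrinking by 1.1%, 3.2% and 6.5% at 2%, 5% and 10%.

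*SE calibration at 20% missing* (separate coding, gap 12.0; reported SE against empirical SD of the estimate). Complete data 1.67 against 1.72; pooled draw 1.38 against 1.44; within-group draw 1.37 against 1.83. Material understatement belongs to reading (b) only.

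*Conditional multiple imputation* (predictive mean matching, five imputations), adjusted baseline gap. Bias −0.02, 0.00, −0.03; coverage 94.5%, 94.5%, 95.3%.

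**The case against.** The strongest case against runs as follows.

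- **Size.** Every rate and gap is assumed. At 2–5% missing, the pooled loss of 0.12–0.60 points is well under 2.4. Losing 2.4 points takes 20% of items imputed for a gap of 12 and 40% for a gap of 6. This stands.
- **Trend.** The 17% rejection rate needs a fivefold rise in missingness and a constant gap. The documents show only that baseline is registered around consultation or treatment start and that later forms go by post. They do not say that baseline answers are checked. If mode matters, it suggests fewer missing items at baseline. In that order, with a narrowing gap, the error is +6% at 2% then 10% and zero at 5% then 10%. This stands too. A reader might infer that the trend could be strongly diluted: 10% then 2% with gaps 12 and 6 gives 10.80 − 5.88 = 4.92 instead of 6.00. That order runs against the only mechanism the documents offer.
- **Existing check.** Under MCAR the non-imputed models are unbiased, though less precise, and would reveal the problem. This is a partial answer. The main estimate would still come from the draw, and no rule covers disagreement between the two.
- **Remedy.** The patient's own item mean recovered the true gap in the large simulation (11.87 against 11.87 at 10% missing, poorer patients skipping more), so item-level multiple imputation may look heavy. A lighter form is acceptable, but a single person-mean fill still carries no imputation uncertainty.

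A reader might also infer that the primary results are affected. The QLQ-C30 outcomes do not use this imputation. Appendix 1 lists NEADL within the geriatric assessment, but Appendix 3 does not define which impairments are counted, so an effect through that count cannot be asserted.

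**Conclusion.** The rule as written does not use the information that its MAR assumption relies on, and it should change. Under a pooled draw, the reported level difference is too small by about the imputed fraction (more if poorer patients skip more), its test and standard-error calibration hardly change, and the trend contrast is exposed when that fraction differs between visits. Under a draw within group and visit, the adjusted difference drifts toward the unadjusted one and intervals are too narrow.

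A reader might add the two together and conclude that the plan both shrinks the difference and understates its standard error. The documents do not support that: the readings exclude each other, and the plan does not say which applies. Nor do they show that the harm is large, since the missing fraction and the NEADL gap are unknown. The simulated sizes rest on MCAR, one stand-in covariate and OLS in place of the mixed model.

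With a secondary outcome, unaffected primary outcomes and a partial check in place, the issue is minor to moderate. It would matter more if item missingness turned out to be 10% or above, or clearly unequal between visits.

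**What to change.** Keep the rule that at least half of the items must be answered. In the main NEADL analysis, replace the unconditional single draw with multiple imputation of the items, or of the scale score from the answered items. Condition on the patient's other NEADL items at that visit, NEADL scores at other visits, visit, treatment intent, visit by intent, age, gender, ECOG PS and cancer type. Fit the mixed model to each completed data set and pool by Rubin's rules. State the item count (20 or 22) on which the half rule operates.

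Report item-missing rates by treatment intent and visit. Keep the non-imputed sensitivity analysis and report how many forms it contains.

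Specifying only that draws are made within visit and treatment intent would remove the average shrinkage of unadjusted differences under MCAR. It would leave the shift in the adjusted difference and the understated standard errors.

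The cost is SAP wording and somewhat more analysis work; no new data are needed. The simulated support for multiple imputation covers the baseline adjusted gap under MCAR, not the trend.

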experienced cancer nurse), based both on the MoCA score and the conversation with the patient, finds reasons to question the patients capability to provide informed consent despite the oncologist's former evaluation, a re-in collaboration with the treating oncologist will be performed before completing the baseline registrations. If the MoCA score is ≤ 16 , the patient's capability to provide informed consent will in any case be re-evaluated. However, since patients with mild to moderate dementia may also have sufficient capability to provide informed consent, no definite MoCA score limit is set for inclusion/exclusion.

Emergency referrals to EBRT is not a defined exclusion criterion. Emergency patients are usually managed as inpatients and may be included if they meet the inclusion criteria. It is, however, a prerequisite that the treating oncologist do not consider the inclusion procedure too burdensome for the patient.

In addition to ask for consent to all study procedures and data collection, the patients will be asked for permission to inform the project contact nurse in the patient's municipality about his/her study inclusion and the planned schedule of his/her follow up registrations.

Non-included patients will be registered by age, gender, diagnosis and cause of exclusion (does not wish to participate/does not fulfil the inclusion criteria/is considered too ill/incapable of participation).

Follow up

The patients will be followed with study specific registrations for 16 weeks after completion of EBRT. As the length of the treatment period may vary from one day (single fraction) to 5-7 (8) weeks for some patients receiving curative treatment, the length of the period from baseline to 16 weeks after treatment will also vary from 16 to 22-23 (24) weeks. With respect to survival, the patients will be followed for two years after completion of EBRT.

At completion of EBRT

At completion of EBRT, the project nurse will perform a repeated GA and hand out the scheduled self-report questionnaire. If the patient prefers to fill in the questionnaire at home, he/she will be given the questionnaire along with a pre-paid return envelope.

~~Patients who have received less than six radiation fractions (about one week of treatment), will only fill in the questionnaire since a new GA after such a short period is likely to add little new information~~

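### Appendix 3 leaves the within-patient covariance and the coding of time open for the trend tests; a random intercept alone could make late-change tests too liberal

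*Combined protocol and SAP*

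**What the plan says.** Appendix 3, Statistical approach, tests the first aim with a linear mixed model having "fixed effects for (non-linear) time, treatment group (curative vs. palliative) and the interaction between the two". The sentence that follows is the whole statement on within-patient dependence: "Random effects for patients will be included". The second aim, the secondary outcomes and the exploratory analyses use similar models; for the second aim the number of geriatric impairments takes the place of treatment intent.

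The hypotheses in Appendix 3 concern trend: "There is a significant difference in trend in outcomes for palliative and curative patients". Hypothesis 2a expects palliative patients to improve in outcomes including "NEADL and pain (PA) within 8 weeks after RT". Hypothesis 2b expects curative patients to worsen and then recover, in outcomes including "fatigue (FA) scores from baseline to 2 weeks after RT. Thereafter the scores will return to baseline values within 16 weeks".

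The QLQ-C30 is collected at baseline, at the end of radiotherapy, and 2, 8 and 16 weeks later. NEADL at the end of radiotherapy is left out of the analysis, so that outcome has four visits. The protocol's Follow up section adds that "the length of the treatment period may vary from one day (single fraction) to 5-7 (8) weeks", so the time from baseline to the last visit runs from 16 to about 24 weeks. The only planned sensitivity analysis concerns non-imputed NEADL.

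**The concern.** A random intercept with independent residuals treats every pair of visits as equally correlated. Two scores 20 weeks apart are then assumed to resemble each other as closely as two scores 2 weeks apart. If correlation falls with the gap, or patients follow different slopes, the model understates the variance of long-range change and overstates that of short-range change.

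The group-by-time interaction is built from those changes, and it carries both main objectives of paper 3. A level that is too high would produce claims of different trends more often than stated. Hypothesis 2b's return to baseline by 16 weeks uses the longest gap, where the error is largest. No planned sensitivity analysis would reveal a wrong covariance.

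**Working it through.** **The plan's own figure.** The protocol's sample size compares two groups at one visit: 10 points, SD 30, 80% power, 5% level (taken as two-sided), ratio 1:1.5. The smaller group is (1 + 1/1.5) × 7.849 × 900/100 = 117.7, so 118 + 177 = 295 against the stated 119 + 178 = 297. This agrees, and it does not depend on the random-effects structure. The documents give no error rate or correlation for the trend models.

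**Inputs.** From Appendix 1: 165 curative and 136 palliative patients. From Appendix 3: five visits. Assumed: visits at weeks 0, 4, 6, 12 and 20 (four weeks of radiotherapy), equal variances, and correlation r(d) falling exponentially with the gap d. Three cases are used: 0.70 to 0.55, 0.75 to 0.475 and 0.80 to 0.40 between gaps of 2 and 20 weeks.

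**Formulas.** Per unit variance, a random-intercept model gives every change between two visits the variance 2(1 − r̄), where r̄ is the mean of the ten pairwise correlations. The true variance is 2(1 − r(d)). The true level of a nominal 5% test is 2{1 − Φ(1.96 √(model/true))}. The factor 1/165 + 1/136 multiplies both variances and cancels, so the result carries over to groups defined by impairment count.

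**Strong case in numbers.** r(d) = 0.864 exp(−0.0385 d) gives r(4) = 0.741, r(6) = 0.686, r(12) = 0.544, r(20) = 0.40 and r̄ = 0.610. Model variance: 2 × 0.390 = 0.781.

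| Change from baseline to | True variance | True/model | True level |
|---|---|---|---|
| End of RT | 0.519 | 0.66 | 1.6% |
| 2 weeks | 0.628 | 0.81 | 2.9% |
| 8 weeks | 0.911 | 1.17 | 7.0% |
| 16 weeks | 1.200 | 1.54 | 11.4% |

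**All three cases (mild, moderate, strong).** The 16-week contrast is at 7.7%, 9.7% and 11.4%. The quadratic-by-group test (2 df, from the matching weighted sum of chi-squares) is at 7.5%, 9.7% and 11.8%. The categorical-time test (4 df) is at 5.3%, 5.7% and 6.3%. With equal correlation, all are at 5.0%.

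**Wider set of truths.** These are random slopes, first-order autoregressive correlation of 0.6-0.8 by visit, and an intercept plus exponential decay, with radiotherapy of 1, 3 or 6 weeks. The dropout column simulates 165/136 patients with assumed losses of 12% (curative) and 42% (palliative) by the last visit. It uses 1,500 runs per case, with a Monte Carlo error of about 0.6 points.

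| Random-intercept test, nominal 5% | Complete data | With dropout |
|---|---|---|
| Quadratic time × group | 5.4-14.1% | 6.5-16.9% |
| Categorical time × group | 5.0-7.4% | 5.0-9.5% |
| Baseline to end of RT | 1.0-4.8% | 1.1-4.0% |
| Baseline to 2 weeks | 2.2-5.9% | 3.5-6.5% |
| Baseline to 8 weeks | 4.7-10.0% | 5.1-10.9% |
| Baseline to 16 weeks | 5.7-13.4% | 7.2-15.2% |

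**Check of the remedy.** One visit-by-visit covariance pools patients with different treatment lengths, so it could itself be wrong. Taking curative courses of 3-8 weeks and palliative courses of one day to 2 weeks (assumed), with the three decay cases and complete data, the unstructured model's overall test and all four contrasts lie between 4.4% and 4.9%.

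**The case against.** The strongest reply is that the plan never commits to a random intercept. Random effects is plural, and the sentence excludes neither slopes nor a residual structure. Nor do the documents show that correlation falls over time; if it does not, every test is exact. Time is only called non-linear, and if that means categorical visits, the overall test is close to nominal. All three points stand, and they make the finding conditional.

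A reader might infer that the plan's p-values and intervals are wrong as written. The text does not support that: it needs a random intercept alone and non-exchangeable correlation, and for the overall test also a low-order curve for time. A reader might also infer that early contrasts in general reject too rarely. That is dependable only for baseline to end of radiotherapy, which no hypothesis singles out. The 2-week contrast in hypothesis 2b can go either way, and the 8-week contrast in hypothesis 2a is near nominal or too liberal.

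The reply does not remove the gap. A random intercept is the simplest model that satisfies the sentence, and equal correlation over 16 to 24 weeks in a cohort the protocol itself calls heterogeneous is a special case. Categorical time does not repair the 16-week contrast. An unstated covariance can also be chosen after the results are seen.

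**Conclusion.** The point holds as a conditional one and should be fixed. Appendix 3 does not state the covariance on which its trend tests depend. If a random intercept alone is fitted and correlation decays or slopes differ, a nominal 5% level can become about 14% (quadratic test) or 13% (16-week contrast) with complete data, and about 17% or 15% with dropout. The lower end is 5%, under equal correlation. The overall test with categorical time stays within about 5-7%, or 9.5% with dropout.

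These sizes rest on assumed correlations, visit times and dropout, because the documents supply no correlations. They show what the open wording permits, not what the trial's data contain. The protocol's sample size is unaffected.

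**What to change.** Replace the sentence on random effects with a full specification: visit as a categorical factor, group and their interaction, an unstructured within-patient covariance, and Kenward-Roger degrees of freedom. For the QLQ-C30 scales this means five visits and 5 × 6/2 = 15 covariance parameters. For NEADL it means four visits and 4 × 5/2 = 10, because the end-of-radiotherapy assessment is excluded. Apply the same wording to the impairment-count models and the exploratory models.

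State a fallback in advance for non-convergence: random intercept and slope with serial correlation, or robust standard errors. A slope without serial correlation is only a partial repair. Under decaying correlation it left the quadratic test at 6.7-9.1% and single contrasts at 3.7-10.7%.

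The cost is plan wording and software options. With about 300 patients the extra parameters are affordable. The downside is somewhat wider intervals for long-range change.
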